Various studies have evaluated the outcomes of different closure devices, however, there are no reports assessing the length of closure times using DERMABOND PRINEO (Ethicon, Johnson and Johnson, Somerville, New Jersey) Knotless Tissue Control Devices during superficial closure in orthopaedic surgery. Huemer et al.(1) performed an observational study of 180 patients who had 224 excisional body-contouring surgeries utilizing Dermabond Prineo for superficial closure. Authors concluded that this closure type enables the surgeon to perform a quick and smooth skin closure. However, 4 patients (1.8%) developed local allergic reactions, which necessitated early removal and topical corticosteroid treatment. Parvizi et al.(2) performed an open, prospective, randomized clinical study of superficial wound closure on 60 patients undergoing abdominoplasty with either Dermabond Prineo or conventional superficial closure. They found significantly lower price (\$134.79 cheaper) and significantly better Hollander Cosmesis Scale scores in Dermabond Prineo cohort. In addition, there was a significantly better cosmetic outcome at 6 and 12 months after surgery. The use of Dermabond Prineo may be able to decrease operative time and costs in other surgical fields, such as orthopedics. Careful patient allergy history is necessary to avoid adhesive allergic reactions.

Regulatory Sponsor:

This study is an Investigator Initiated research trial. Each study site will be considered its own regulatory sponsor and is responsible for internal data monitoring and any study reporting required by ClinicalTrials.gov.

Study Design:

In this prospective pilot study examining the superficial closure during total knee arthroplasty, active subjects will receive the STRATAFIX Spiral Knotless Tissue Control Device for subcuticular closure in addition to DERMABOND PRINEO (Ethicon, Johnson and Johnson, Somerville, New Jersey) system for dermal closure. The control subjects will receive staples (standard-of-care).

The purpose of this study is to compare end points (see below):

- **The primary endpoint of the study** will be cosmesis observation using the modified Hollander scale (Table1).
- **Secondary endpoints** will examine: wound closure time, patient satisfaction with wound appearance, wound related complications, cost comparison including time and materials

As a pilot study, hypothesis testing will not be performed.

Post-operatively, patients will be assessed at clinic visits at 6 weeks and 3 months. At these time points, we will assess (**Table 2**):

- Incidence of any wound complications
- Wound appearance using the Hollander cosmesis questionnaire (**Table 1**)
- Patient satisfaction with wound appearance using visual analogue scale (VAS)

Table 1. Hollander cosmesis questionnaire	
Stepoff borders	0 for yes, 1 for no
Contour irregularity – puckering	0 for yes, 1 for no
Scar width – greater than 2mm	0 for yes, 1 for no
Edge inversion – sinking, curling	0 for yes, 1 for no
Inflammation – redness, discharge	0 for yes, 1 for no
Overall cosmesis	0 = poor, 1 = acceptable

Table 2: Research Procedures				
REQUIRED STUDIES	Pre-Op	Intra-operative	6 weeks post-op	3 months post-op
Informed Consent	x			
Length of surgery		x		
Length of closure time		x		
Amount of suture material used		x		
Surgeon experience level		x		
Incidence of wound complications			x	x
Hollander cosmesis questionnaire			x	x
Patient satisfaction with wound appearance (VAS)			x	x

Methods

- A prospective randomized pilot study

Sample

- 60 subjects for a pilot study

Inclusion Criteria:

1. Males and females, between the ages of 18 to 80 years at the time of signing the informed consent document.
2. Understand and voluntarily sign an informed consent document prior to any study-related assessments/procedures are conducted.
3. Able to adhere to the study visit schedule and other protocol requirements.
4. Able to fluently speak and understand the local language
5. If female, is nonpregnant (negative pregnancy test results at the baseline/randomization visit) and nonlactating.
6. End-stage osteoarthritis patients planning to undergo primary total knee arthroplasty
7. BMI less than 40 kg/m²

Exclusion Criteria:

1. BMI greater than or equal to 40 kg/m²
2. History of known bleeding disorder

3. History of medical co-morbidity that may result in poor wound healing (ie. diabetes mellitus, peripheral vascular disease)
4. Patients <18 or >80 years of age
5. Patients who are prisoners
6. Mentally unable to sign informed consent
7. Has an uncontrolled illness that, in the opinion of the investigator, is likely to cause the patient to be withdrawn from the trial or would otherwise interfere with interpreting the results of the study.

Screening and Recruitment: Informed Consent

Informed consent will be obtained by one of the study coordinators/co-investigators during a clinical visit prior to procedure in the privacy of an examination room or an office. Patients will be informed about the study and inquired about their interest to participate. A consent document will be given and key parts of the research study will be explained in lay-terms to the patient to ensure full understanding. Any questions regarding the research study will be answered at that time. It will be emphasized that participation is voluntary. Those patients who are willing to participate will be asked to sign the consent document along with the consenting researcher. A signed copy of the consent document will be handed to the patient while another copy is kept in their study file.

In the event that an approach prior to the day of surgery is not feasible, same day of procedure consenting will be attempted. Patients will be contacted by telephone (see phone script), and those interested in participating in the study will be informed about what is involved, the follow-up visit, and that participation in the study is strictly voluntary, and will not affect the scheduling of their upcoming surgery. If the patient is interested in participating, the patient can be either mailed or emailed a copy of the informed consent form, and then arrangements will be made to complete the informed consent process prior to the patient being taken back into the preoperative area on the day of surgery. The patient will be asked to come to the hospital on the day of surgery earlier than the time they were told to arrive by surgical scheduling in order to make sure there will be adequate time to discuss the study, including what is involved, risks, benefits, and alternatives. We do not believe that an eventual approach on the same day of procedure would represent an added stress for the patient or delay the start of the procedure. Similar to obtaining informed consent prior to the day of procedure, the process will occur in a

private setting with ample time to discuss the study's implications, risks, benefits, and alternatives. No procedures or tests will be conducted on the screening visit after consenting the patient.

Randomization procedures:

Patients will be randomized to either arm of the study as follows: sealed envelopes in a random order will be used to place study participants in either the active arm or in the control arm of the study. Patients will be randomized in a one to one ratio. At the commencement of each arthroplasty, a random envelope will be drawn which dictated the type of suture to be used, thus blinding the patients to the type of suture they received.

Research Procedure:

A medial parapatellar approach will be performed. All closures will be performed in 3 layers, with the knee in approximately 90° of flexion to minimize potential imbrication of the capsule. For the traditional closure (control group), the arthrotomy (deep layer) is repaired using number 1 Vicryl followed by closure of the intermediate layer with a 2-0 Vicryl and the skin will be closed with staples (Standard of care).

For the active arm of the study, the arthrotomy (deep layer) is repaired using number 1 Vicryl, the subcutaneous layer will be then closed with simple interrupted knots using number 2-0 braided absorbable sutures (Vicryl), followed by closure of the subcutaneous layer using a STRATAFIX Spiral Knotless Tissue Control Device in addition to DERMABOND PRINEO (Ethicon, Johnson and Johnson, Somerville, New Jersey) system for dermal closure. (See table 3).

Closure with the bidirectional barbed suture involves starting at the midpoint of the wound and proceeded simultaneously both proximally and distally to the ends. At the ends of the wounds, the suture is backstitched at this subcuticular level (2-3 throws) toward the midpoint for further reinforcement before bringing the needle out through the skin; the suture is then cut flush with the skin tissue at its free end. With each throw, the leading end of the suture is pulled with only enough tension to engage the barbs with the surrounding tissue, thereby locking the wound edges into approximation. As with the traditional closure and in concordance with our routine protocol, skin will be closed with staples.

Table 2: Suture Type for Closure Following Total Knee Arthroplasty.		
Layer	Control Group	Active Group
Capsule	Vicryl #1 (J947H#1)	Vicryl #1 (J947H#1)
Subcutaneous	Vicryl 2.0 (J945H 2-0)	Vicryl 2.0 (J945H 2-0)
Subcuticular	Staples	STRATIFIX Spiral Knotless tissue control device (undyed)
Skin		DERMABOND PRINEO

Patient Protection:

All data collection sheets will be de-identified. All patients will be assigned a study ID. All data collected will be entered into Excel sheet and stored on Cleveland Clinic secure computers. Only members of the study team (listed on the IRB application) will have access to protected health information of patients included in this study.

Safety Monitoring Plan

Procedural safety will be documented in this study through patient and surgeon reported adverse events. AEs will be documented for all cases in this study. An Unanticipated Problem involving risks to participants or others is any event that (1) is unforeseen, (2) caused harm or placed a person at increased risk of harm, and (3) is related to the research procedures.

An Adverse Event (AE) is any untoward or unfavorable medical occurrence, including any abnormal sign (for example, abnormal physical exam or laboratory finding), symptoms, or disease. Adverse events can encompass both physical and psychological harms. An Internal Adverse Event (AE) is an untoward medical occurrence, which occurs to participants in research conducted by Cleveland Clinic and/or Cleveland Clinic is the IRB of record. External Adverse Event (AE) is an untoward medical occurrence experienced by subjects enrolled at other institutions for the same study approved at Cleveland Clinic or a different study using the same study drug/device. A Serious Adverse Event (SAE) is any adverse experience that results in any of the following outcomes:

- Death
- A life-threatening experience
- Inpatient hospitalization or prolongation of existing hospitalization

- A persistent or significant disability/incapacity.
- A congenital anomaly/birth defect
- Important medical events that may not result in death, be life-threatening, or require hospitalization may be considered a serious adverse drug experience when, based upon appropriate medical judgment, they may jeopardize the patient or subject and may require medical or surgical intervention to prevent one of the outcomes listed in this definition.

An Unexpected Adverse Event means any AE not previously known or included in the current Investigator's Brochure, consent form or other risk information.

Related/Possibly Related means there must be reasonable evidence to suggest the event was caused by the drug, device or investigational intervention.

1. Internal Serious Adverse Events (events that occur to participants enrolled in research being conducted by Cleveland Clinic or when Cleveland Clinic is the IRB of record) must be promptly reported to the IRB using the IRB AE Report Form within 10 working days from discovery/awareness which meet any of the following criteria as assessed by the PI/Co-I:

- a) Serious, Unexpected and Related/Possibly Related.
- b) AE's determined to be occurring at a significantly higher frequency or severity than expected.
- c) Other Unexpected AE's, regardless of severity, that changes the risk benefit ratio of the study and results in changes to the Research Protocol or Informed Consent process/document.

All Internal SAEs are also reported at continuing review using the AE Summary Log.

2. External Serious Adverse Events (events experienced by subjects enrolled at other institutions for the same study approved at Cleveland Clinic or a different study using the same study device/drug) are reportable to the IRB using the IRB AE Report Form within 10 working days from discovery/awareness when:

- a. The External SAE report includes reasonable evidence as assessed by a central monitoring entity [Coordinating or Statistical Center, or a Data Safety Monitoring Board (DSMB) or Data Monitoring Committee (DMC)] that the event is Serious, Unexpected, and Related/Possibly Related AND places the subjects or others at a greater risk of physical or psychological harm than was previously known or recognized. This will require a change in the protocol and/or consent document.

- b. External SAE reports provided by the Sponsor to the investigator indicating the event is Serious, Unexpected and Related/Possibly related but without reasonable evidence or DSMB/DMC determination of greater risk are not reportable to the IRB within the 10 day window. Without Sponsor evidence or assessment the implications of the event cannot be determined by the research team and therefore need not be reviewed. These SAE' shall be placed on the AE Summary log to be submitted at the annual continuing renewal.

3. DEATHS are to be reported to the IRB using the IRB AE Report Form according to the following guidelines:

a) Internal Death:

- Related/possibly related whether expected or unexpected– within 5 working days from discovery/awareness
- Not related and expected – at time of continuing review
- Not related and unexpected – at time of continuing review except cancer studies.
- Cancer: Not related and unexpected within 10 working days from discovery/awareness

b) External Death:

Related/possibly related and unexpected – within 5 working days from discovery/awareness not related whether expected or unexpected – at time of continuing review related/possibly related and expected – at time of continuing review

c) ALL Deaths are also reported at time of continuing review using the AE summary log.

4. Non-serious Adverse events (Internal and External) that are both Related/Possibly related and unexpected are reported on the AE Summary Log at time of continuing review to assess trends.

5. An IRB staff (a qualified, licensed practitioner assigned to this function by the IRB chair and IRB Executive Director) reviews Adverse Event Reports to determine whether they represent Unanticipated Problem Involving Risks to Participants or Others. Events that are assessed, by either the IRB Staff or Investigator, to place subjects or others at a greater risk of harm than was previously known or recognized, or changes the risk/benefit ratio of the study, or requires a change in the protocol and/or consent document are referred to Full Board for review under Policy #70. Events that do not involve risk to Participants or Others or changes to the

informed consent or protocol do not require further review. Investigators are informed of the determination and the IRB file is updated.

6. The AE Summary Log is reviewed by the IRB at the time of continuing review to identify trends in frequency and severity which may impact subject safety.

This study is an Investigator Initiated research trial. Each study site will be considered its own regulatory sponsor and is responsible for internal data monitoring and any study reporting required by ClinicalTrials.gov.

Data Analysis:

Unless otherwise indicated, all testing of statistical significance will be two-sided, and a difference resulting in a p-value of less than or equal to 0.05 will be considered statistically significant. Also, after each analysis, General Linear Models (GLM) will be used to control for possible confounders, including BMI, gender, age and ethnicity.

References

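### The protocol calls an allergy history necessary before adhesive use, but no eligibility criterion or documented pre-randomisation check puts this into effect

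*Combined protocol and SAP*

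**What the plan says.** The background text at the start of the protocol describes an observational study of 180 patients and 224 body-contouring procedures closed with DERMABOND PRINEO, in which "4 patients (1.8%) developed local allergic reactions, which necessitated early removal and topical corticosteroid treatment". It ends with the precaution "Careful patient allergy history is necessary to avoid adhesive allergic reactions".

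The Inclusion Criteria and Exclusion Criteria each contain seven items. None names allergy, hypersensitivity or adhesive sensitivity. The two nearest are:

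- Exclusion 3: "History of medical co-morbidity that may result in poor wound healing (ie. diabetes mellitus, peripheral vascular disease".
- Exclusion 7, which begins "Has an uncontrolled illness that, in the opinion of the investigator, is likely to cause the patient to be withdrawn".

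One other pre-randomisation check is written into eligibility, in inclusion 5: "If female, is nonpregnant (negative pregnancy test results at the baseline/randomization visit) and nonlactating".

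Under Randomization procedures, allocation takes place in theatre: "At the commencement of each arthroplasty, a random envelope will be drawn which dictated the type of suture to be used". No contraindication check comes before it, and there is no rule for a patient who cannot receive the adhesive. The Research Procedure section gives DERMABOND PRINEO to the whole active arm. The Safety Monitoring Plan adds that "AEs will be documented for all cases in this study".

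**The concern.** The standard here is the protocol's own. It names a hazard of the study device, names the precaution and calls that precaution necessary. The sections that decide who enters the trial and who receives the device do not carry the precaution forward. A site that followed the eligibility list exactly could enrol a patient with a known adhesive allergy and apply the adhesive.

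The stake is patient safety. Adverse event documentation and the wound assessments at 6 weeks and 3 months detect a reaction after exposure; they do not prevent one. Timing adds a practical difficulty. Because the envelope is drawn as the operation begins, an allergy noticed only then forces the team to improvise or to depart from the allocation. No bias in the Hollander score or in any other analysis is alleged.

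**Working it through.** **1. Does any criterion reach a known adhesive allergy?**

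| Place in the protocol | What it covers | Reaches a past contact allergy? |
|---|---|---|
| Inclusion 1–7 | Age, consent, adherence to visits, language, pregnancy and lactation, end-stage osteoarthritis, BMI | No |
| Exclusion 1, 2, 4, 5, 6 | BMI, bleeding disorder, age, prisoners, capacity to consent | No |
| Exclusion 3 | Co-morbidity that impairs wound healing; examples are diabetes and peripheral vascular disease | Not on a plain reading |
| Exclusion 7 | Uncontrolled illness, at the investigator's discretion | No; a past contact allergy in a well patient is not an uncontrolled illness |
| Randomization procedures | Envelope drawn at the start of surgery | No check stated |
| Safety Monitoring Plan | Recording and reporting of adverse events | Acts only after exposure |

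The Screening and Recruitment section also says "No procedures or tests will be conducted on the screening visit after consenting the patient". Little rests on this sentence, because a question about allergies is not clearly a test. The point depends on the missing criterion and the missing documented check.

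**2. The protocol's own rate.** Inputs from the background text: 4 patients with reactions, 180 patients, 224 procedures.

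- Per procedure: 4/224 = 1.79%, which reproduces the stated 1.8%. Exact (Clopper-Pearson) 95% CI 0.49% to 4.51%.
- Per patient: 4/180 = 2.22%, exact 95% CI 0.61% to 5.59%.

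The stated percentage therefore uses procedures as its denominator, although the count is of patients. Both are carried forward.

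**3. Scale in this trial.** Sixty subjects allocated one to one give about 30 in the active arm. Assume that the cited rate *p* carries over to knee arthroplasty.

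- Expected reactions of any kind, 30*p*: 30 × 0.01786 = 0.54 (95% CI 0.15 to 1.35) per procedure; 30 × 0.02222 = 0.67 (0.18 to 1.68) per patient.
- Chance of at least one, 1 − (1 − *p*)^30: 42% and 49% respectively.

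**4. How many would a history prevent?** The protocol does not say whether any of the four patients had a known allergy, or whether that study screened for it. The preventable share *s* is therefore an assumption, shown over its full range. Reactions prevented = 30 × *p* × *s*:

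| Assumed share *s* | Per-procedure rate | Per-patient rate |
|---|---|---|
| 0 | 0 | 0 |
| 0.25 | 0.13 | 0.17 |
| 0.5 | 0.27 | 0.33 |
| 1 | 0.54 | 0.67 |

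The documents support no narrower range.

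**The case against.** The strongest reply has four parts.

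- **Routine care.** An allergy history is ordinary practice before elective surgery, and this short protocol does not describe routine pre-operative work-up at all. The consent form and phone script are not visible and may contain an allergy question. This stands as a limit: the text does not show that no history is taken. It does not close the gap, because nothing visible ties such a history to eligibility or allocation, and neither a consent form nor a phone script is an eligibility criterion.
- **Silence elsewhere is weak evidence.** Table 2 (Research Procedures) lists only consent before surgery and omits even the pregnancy test that inclusion 5 requires. This is correct, so the absence of an allergy item from that table shows little. The criteria lists, however, are complete and numbered without gaps, and the omission there is clear.
- **The rate does not measure the defect.** The figure of 1.8% counts all local reactions in a different kind of surgery. It says nothing about how many patients have a known allergy, and a history cannot identify a patient who is unaware of one. This also stands. The figures in the working give scale only, and 0.54 to 0.67 is a ceiling at the point estimates.
- **The harm is small.** The reactions described were local and treatable, and adverse events are recorded for every case. That argues against a higher priority. It does not justify leaving a precaution that the protocol itself calls necessary out of the eligibility rules.

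**Conclusion.** The concern holds. The visible protocol has no eligibility criterion and no documented pre-randomisation check for adhesive allergy, so a patient with a known allergy is eligible for the active arm as written. This conclusion rests on the text and does not depend on any rate.

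The likely size is small. At the cited point estimates, between none and less than one reaction would be prevented among about 30 active-arm patients. That assumes the body-contouring rate applies to knee arthroplasty, and the preventable share is unknown. Confidence in the textual finding is high. The change should be made, on safety grounds alone and because it costs very little.

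**What to change.** Add an exclusion criterion for known allergy or hypersensitivity to the adhesive or its components, with the component list confirmed against the device labelling. Require a documented allergy history for every candidate, completed before the envelope is drawn and preferably at consent. Asking all candidates before allocation applies the same eligibility rule to both groups and avoids withdrawals after allocation in the active arm only.

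The cost is one line in the criteria and one recorded question per patient. The downside is that a few candidates are screened out. The documents give no prevalence of known adhesive allergy; as a bare assumption carrying little weight, 0.5% to 5% would mean 60 × 0.005 = 0.3 to 60 × 0.05 = 3 of 60. Because the check comes before allocation, those candidates can be replaced without changing the target of 60.

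### Incision length is neither recorded nor named as a covariate, so length-driven variation in closure time stays in the error term; recording it is a cheap precision gain on secondary endpoints only.

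*Combined protocol and SAP*

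**What the plan says.** Study Design lists the secondary endpoints as "wound closure time, patient satisfaction with wound appearance, wound related complications, cost comparison including time and materials". Closure time is thus an endpoint in its own right and also an input to the cost comparison.

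The table headed Table 2: Research Procedures has four items specific to the operation: duration of surgery, "Length of closure time", suture material used, and the surgeon's experience level. Wound or incision length is not among them. It appears nowhere else in the document, and no standard incision length is set.

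Research Procedure describes the barbed-suture closure as "starting at the midpoint of the wound and proceeded simultaneously both proximally and distally to the ends". The suture-type table in the same section gives both arms the same capsule and subcutaneous sutures. The arms differ only above those layers.

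Data Analysis plans general linear models to control for possible confounders, "including BMI, gender, age and ethnicity". The sample is "60 subjects for a pilot study", and "Patients will be randomized in a one to one ratio".

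**The concern.** A longer wound takes longer to close. The description of the barbed suture shows this directly for the active arm, and it is a reasonable inference for a row of staples. If incision length varies between patients, part of the spread in closure time reflects the wound and not the closure method. An analysis that knows the length can remove that part; one that does not must carry it as noise.

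The covariate list opens with a word that leaves room for additions, but a variable that was never measured cannot be added. BMI and gender may carry some information on length, though only indirectly.

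A related gap is that closure time has no stated start or stop. Study Design presents the trial as one of superficial closure. Time spent on the two deeper layers, which are the same in both arms, would say nothing about the devices being compared.

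At stake is the width of the interval for the closure-time difference and, through it, the time part of the cost comparison. This holds whichever statement on testing governs. Study Design says "As a pilot study, hypothesis testing will not be performed", in which case the estimate and its interval are the main output. Data Analysis says "all testing of statistical significance will be two-sided, and a difference resulting in a p-value of less than or equal to 0.05" will count as significant, in which case lost precision is lost power. The two statements need reconciling, but that is a separate matter.

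**Working it through.** **The plan's own figure.** The total of 60 comes without power, effect size, SD or dropout, so there is no sample-size calculation to reproduce. With 1:1 allocation, 60 / 2 = 30 per arm.

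**Inputs from the documents.** n = 30 per arm; two-sided 5% level, hence a 95% interval.

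**Assumed input.** r, the within-arm partial correlation of incision length with closure time after the planned covariates. The documents give no value, so a range is shown.

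**Formulas**, in units of the within-arm SD of closure time:

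- Without incision length: half-width = t(0.975, 58 df) × √(2/30) = 2.0017 × 0.2582 = 0.517.
- With incision length: half-width = t(0.975, 57 df) × √(2/30) × √V, where V = (1 − r²) × (1 + 1/(2n − 5)) = (1 − r²) × (1 + 1/55). The second factor is the small-sample price of estimating one covariate slope.

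Worked example at r = 0.5: V = 0.75 × 1.0182 = 0.764, and 2.0025 × 0.2582 × √0.764 = 0.452. The narrowing is 1 − 0.452/0.517 = 12.6%.

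| r (assumed) | V | Half-width | Change from 0.517 |
|---|---|---|---|
| 0.1 | 1.008 | 0.519 | slightly wider |
| 0.13 | 1.001 | 0.517 | none |
| 0.3 | 0.927 | 0.498 | 4% narrower |
| 0.5 | 0.764 | 0.452 | 13% narrower |
| 0.6 | 0.652 | 0.417 | 19% narrower |

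**Break-even.** V = 1 when r² = 1/56 = 0.0179, so r is about 0.13. Below that, the covariate costs as much as it returns, or more.

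**Limits of the calculation.** It adds one covariate to a plain two-arm comparison. With the planned covariates already in the model, the SD is the residual SD after them and both half-widths have fewer degrees of freedom, so the percentages are approximate. One common slope of time on length is assumed for both arms.

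**The case against.** The strongest reply is that this is a preference and not a defect. Nothing in the plan contradicts itself on this point, no arm is favoured, only secondary endpoints are touched, and almost any trial could record one more prognostic variable. That stands as a limit on severity. It does not remove the point, because closure time is the gap that the background names for orthopaedic superficial closure, and the missing measurement cannot be obtained later.

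A second reply is that the gain is unknown. That also stands. BMI, gender and age are already to be adjusted for and may absorb part of the effect, so only the partial correlation counts, and the gain could be nil.

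Third, the length mechanism is documented for the barbed suture only. Time per centimetre may differ for staples, so a common slope is an assumption. If suture and mesh are counted in whole units, which the documents do not state, material cost would follow length only in steps and the gain there may be smaller.

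Fourth, the envelope is drawn as the operation begins, so a reading before the draw has to fit that sequence. This is a fair constraint, and the fix has to allow for it.

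A reader might go further and infer that the closure-time comparison is biased. The documents do not support that: allocation is randomised, so incision length is balanced in expectation, and what remains is variance. A reader might also infer that the deeper layers are being timed and swamp the signal. The documents do not say that they are timed; they leave the interval undefined.

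**Conclusion.** The point holds as a low-cost improvement, limited to precision and to secondary endpoints: mainly closure time, and less surely material cost. The facts are firm: incision length is not collected, not standardised and not a named covariate.

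The size is not firm. It runs from no gain at a partial correlation of about 0.13 or below to an interval about 19% narrower at 0.6. It rests on the assumed r, a common slope in both arms and 30 analysed patients per arm. It would be tempting to turn this into a definite number of subjects saved, or to say that a later trial would be mis-sized. The documents support neither: they give no SD or correlation, and they name no later trial or sizing aim. The primary endpoint, the modified Hollander score, is outside this point.

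**What to change.** 1. Add incision length (cm) to the intra-operative column of Table 2: Research Procedures. Measure it in one standard way and one stated knee position, on the marked incision line before the envelope is drawn. Because the draw is made as the operation begins, state the order of the two steps. If a reading before the draw is not feasible, take it before closure starts.
2. In Data Analysis, pre-specify incision length as a covariate in the model for closure time. Use it for material cost only as a supplementary analysis.
3. Record a time stamp when the 2-0 Vicryl layer common to both arms is complete. Define the closure-time endpoint as superficial closure time, from that stamp to the end of skin closure.

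The cost is one ruler reading and one time stamp per case, and one degree of freedom in the model. If the partial correlation turns out very low, the interval will be marginally wider (0.519 against 0.517 SD at r = 0.1). No added visit is needed.
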